5.1.2 Hypotheses and Statistical Methods for Secondary Objectives

5.1.2.1 Hypotheses

Non-inferiority on CYD dengue vaccine after three doses

The objective was to demonstrate that the humoral immune response of 3 doses of CYD dengue vaccine with the first dose administered concomitantly with the Tdap booster dose is non-inferior to the humoral immune response of 3 doses of CYD dengue vaccine administered sequentially with the Tdap booster dose administered 28 days before the first dose of CYD dengue vaccine.

Due to early termination study, this analysis will not be done (cf. section 5.7)

5.1.2.2 Statistical Methods

Non-inferiority on CYD dengue vaccine after 3 doses

Analysis on the 3rd dose are not applicable due to the early termination of the study (cf. section 5.7)

Descriptive analysis on CYD dengue vaccine and Tdap vaccine immunogenicity*

No hypotheses will be tested. Immunogenicity point estimates and their 95% CI will be presented for each and any group and by baseline dengue status, before and after the first injections for CYD dengue vaccine and before and after the booster vaccination for Tdap.

A complementary analysis on CYD dengue vaccine and Tdap vaccine immunogenicity after each dose will be conducted for each and any group according to the age groups (9 to 11 years, 12 to 17 years, 18 to 45 years and 46 to 60 years).

* Analysis on the 3rd dose are not applicable due to early termination of study (cf. section 5.7)

In addition, the booster response against pertussis components (PT, FHA, PRN, and FIM2+3) will be calculated based on Ab concentration rises between pre- and post-vaccination defined as:

- A post-vaccination Ab concentration $\geq 4 \times$ the lower limit of quantification (LLOQ) when pre-vaccination concentration is $< \text{LLOQ}$
- A post-vaccination Ab concentration $\geq 4 \times$ pre-vaccination Ab concentration when pre-vaccination concentration is $\geq \text{LLOQ}$ but $< 4 \times \text{LLOQ}$
- A post-vaccination Ab concentration $\geq 2 \times$ pre-vaccination Ab concentration when pre-vaccination concentration is $\geq 4 \times \text{LLOQ}$

Safety

All analyses will be descriptive; no hypotheses will be tested. Safety will be assessed for all subjects after the booster dose of Tdap vaccine and after each and any dose of CYD Dengue vaccine and by baseline dengue status.

A complementary analysis will be conducted for each group according to the age groups (9 to 11 years, 12 to 17 years, 18 to 45 years and 46 to 60 years).

A complementary analysis after the first CYD dengue vaccine will be conducted for each and any group in the non-immune or undetermined dengue subjects at baseline.

5.2 Analysis Sets

Four analysis sets will be used: the Per-Protocol Analysis Set (PPT and PPC for Tdap and CYD dengue vaccine respectively), the Full Analysis Set (FAS), and the Safety Analysis Set (SafAS).

5.2.1 Full Analysis Set

The FAS is defined as the subset of subjects who received at least one dose of the study vaccines.

Subjects will be analyzed by baseline dengue status and by the group to which they were randomized.

5.2.2 Per-Protocol Analysis Set

Two PPASs will be defined: one for Tdap (PPT) and one for CYD dengue vaccine after first dose (PPC).

The list of deviations leading to exclusion from the PP populations was adapted to exclude dengue seronegative subjects at baseline from the populations. Further details can be found in Section 5.7

PPT

The subjects presenting with at least one of the following relevant protocol deviations will be excluded from the PPT:

- Subject did not meet all protocol-specified inclusion criteria or met at least one of the protocol-specified exclusion criteria
- Subject had dengue seronegative status at baseline
- Subject did not complete the vaccination schedule (at V02 for Group 1, V01 for Group 2)
- Subject received a vaccine other than the one that he/she was randomized to receive (at V02 for Group 1, V01 for Group 2)
- Administration of vaccine was not done as per-protocol (site and route of administration) (at V02 for Group 1, V01 for Group 2)
- Subject did not receive vaccine in the proper time window (at V02 for Group 1)
- Subject did not provide after Tdap injection a post-dose serology sample in the proper time window or a post-dose serology sample was not drawn (V03 for Group 1, V02 for Group 2)
- Subject received a protocol-prohibited medication (prohibited therapies/medications/vaccines are indicated in the Protocol Section 6.7) (until V03 for Group 1, V01 to V02 for Group 2)
- Subject's serology sample did not produce a valid test result, i.e., no Tdap Ab concentration available (at V03 for Group 1, V02 for Group 2)

PPC

The subjects presenting with at least one of the following relevant protocol deviations will be excluded from the PPC:

- Subject did not meet all protocol-specified inclusion criteria or met at least one of the protocol-specified exclusion criteria
- Subject had dengue seronegative status at baseline
- Subject did not complete the vaccination schedule (at V02 for Group 1, at V01 and V02 for Group 2)
- Subject received a vaccine other than the one that he/she was randomized to receive (at V02 for Group 1, at V01 or V02 for Group 2)

- Administration of vaccine was not done as per-protocol (site and route of administration) (at V02 for Group 1, at V01 and V02 for Group 2)
- Subject did not receive vaccine in the proper time window (at V02 for Group 1 and Group 2)
- Subject did not provide after the first CYD dengue vaccine injection a post-dose serology sample in the proper time window or a post-dose serology sample was not drawn (at V03 for Group 1 and Group 2)
- Subject received a protocol-prohibited medication (prohibited therapies/medications/vaccines are indicated in the Protocol Section 6.7) (until V03 for Group 1 and Group 2)
- Subject's serology sample did not produce a valid test result, i.e., no Neutralizing Ab titers against any of the four parental dengue virus serotypes of CYD dengue vaccine available (at V03 for Group 1 and Group 2)

5.2.3 Safety Analysis Set

The SafAS is defined as the subjects who have received at least one dose of the study vaccines. All subjects will have their safety analyzed after each dose according to the vaccine they actually received, and after any dose according to the vaccine received at the first dose.

Safety data recorded for a vaccine received out of the protocol design will be excluded from the analysis (and listed separately).

Note: Subject will be included in the “any dose” analysis according to the 1st dose received that corresponds to a protocol group.

5.2.4 Other Analysis Set

Randomized subjects

A randomized subject is a subject for whom an injection group has been allocated.

5.2.5 Populations Used in Analyses

The main immunogenicity analyses (non-inferiority tests) will be performed on the per protocol analyses sets PPT and PPC respectively for Tdap and CYD dengue vaccine comparisons For Tdap and will be confirmed on the FAS (only Dengue Immune subjects for CYD dengue vaccine). The subjects will be analyzed by the group to which they were randomized.

All other immunogenicity analyses will be performed on the FAS by baseline dengue status. Subjects will be analyzed by the vaccine group to which they were randomized.

The SafAS will be performed on the safety analysis set by baseline dengue status. Subjects will be analyzed according to the vaccine they actually received.

5.3 Handling of Missing Data and Outliers

5.3.1 Safety

No replacement will be done.

In all subject listings, partial and missing data will be clearly indicated as missing.

5.3.1.1 Immediate

For unsolicited non-serious systemic AEs, a missing response to the “Immediate” field will be assumed to have occurred after the 30-minute surveillance period and will not be imputed.

For SAEs, missing or partially missing elapsed time from last vaccination recorded will remain missing and not be imputed. Such SAEs will not be considered as immediate.

5.3.1.2 Causality

Missing causality (relationship) for unsolicited non-serious AEs and SAEs will be considered at the time of analysis as related to vaccination.

5.3.1.3 Measurements

Partially missing temperatures will be handled as described in Section 4.4.1.1.1.

5.3.1.4 Intensity

For solicited reactions, missing intensities will be handled as described in Section 4.4.1.1.1. For unsolicited non-serious AEs, missing intensities will remain missing and will not be imputed.

5.3.1.5 Start Date and Stop Date

Missing or partially missing start dates for unsolicited AEs will remain missing and not be imputed. If either the start or stop date is missing or partially missing, the time to onset will be considered to be missing. Nevertheless unsolicited AEs with missing time to onset will be included in analyses according to the visit collected.

Missing or partially missing stop dates for AEs (solicited reactions and unsolicited AEs) will remain missing and not be imputed.

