4.4.1.2.3 Time of Onset

Time to onset in days following the vaccination will be computed as follows:

- Time to onset = start date – date of previous vaccination

If the start date of the AE is the same as the last vaccination date, then the onset is “0”.

If one of the dates is partially missing, time to onset will be considered as “Missing”. Events that occur before vaccination (negative time to onset) will not be included in the analyses but will be listed separately. The unsolicited non-serious AEs will be analyzed within 28 days after vaccination, which corresponds to AEs with a time to onset between 0 and 28 days after vaccination or missing. An AE with missing time to onset will be considered to have occurred just after the vaccination indicated by the visit number, so will be included in these tables.

Time to onset will be displayed by period as follows:

- D0-D3
- D4-D7
- D8-D14

- $\geq D15$
- Missing

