4.4.1.2.4 Duration

The duration will be computed as: Duration = stop date of event - start date of event + 1.

If start or stop dates are unfilled (“blank”) or missing (contain “MD”) or ongoing is ticked, then the duration will be considered as “Missing.”

If the start date of the AE is the same as the last vaccination date, then the duration is 1 day.

Duration will be displayed by period as following:

- 1-3 days
- 4-7 days
- 8-14 days
- 15 days or more
- Missing

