4.4.1.3.2 Time of Onset

Time to onset will be computed using the same methodology as for unsolicited non-serious AEs described in Section 4.4.1.2.3.

SAEs will be analyzed throughout the study using the following periods:

- Within 28 days after each/any injection
- During the study (i.e., all SAEs occurred during the study)

An SAE with missing time of onset will be considered to have occurred after the vaccination indicated by the visit number, so will be included in these tables.

Note: SAEs that occurred before vaccination (negative time to onset) will not be included in analysis, but will be listed separately.

Note for SAEs: Elapsed time from last vaccination recorded will be calculated if the SAE occurred within 24 hours of vaccination.

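### SAP 5.3.1.5 makes time to onset missing when only the stop date is missing, contradicting 4.4.1.2.3; if followed, it would put SAEs with known late onset into the 28-day tables

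*SAP*

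**What the plan says.** Four parts of the SAP bear on the point.

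- **4.4.1.2.3 (unsolicited non-serious AEs)** gives the formula "Time to onset = start date – date of previous vaccination" and makes the result missing if one of the dates is partial. It defines the 28-day analysis as one "which corresponds to AEs with a time to onset between 0 and 28 days after vaccination or missing".
- **4.4.1.3.2 (SAEs)** adopts the same derivation: "Time to onset will be computed using the same methodology as for unsolicited non-serious AEs described in Section 4.4.1.2.3". It lists two periods, 28 days after injection and the whole study. An SAE whose onset is missing is placed by its visit number, "indicated by the visit number, so will be included in these tables".
- **4.4.1.2.4 (duration)** is where the stop date is used. Duration is stop date minus start date plus 1, and is missing if either date is blank or coded MD, "or ongoing is ticked, then the duration will be considered as" missing.
- **5.3.1.5 (missing dates)** says "If either the start or stop date is missing or partially missing, the time to onset will be considered to be missing". It then adds "Nevertheless unsolicited AEs with missing time to onset will be included in analyses according to the visit collected". Neither start nor stop dates are imputed.

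**The concern.** For an event with a complete start date and an incomplete stop date, 4.4.1.2.3 gives a number of days and 5.3.1.5 gives missing. Both rules cannot be programmed. A missing onset does not take the event out of the tables; it places the event in them by visit.

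For SAEs, which are collected long after Day 28, the choice of section can therefore decide whether an event falls inside or outside the 28-day table. It also decides whether the event enters the 28-day summaries of seriousness and outcome in SAP 4.4.1.4.2 and 4.4.1.4.3. The error would move late events into the window closest to vaccination. For non-serious events, a known onset would be reported in the missing category.

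**Working it through.** The plan states no figure to reproduce, so the check applies each rule to the same events.

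**Inputs**

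- Rule A (SAP 4.4.1.2.3): onset = start date − previous vaccination date; missing only if one of those two dates is incomplete.
- Rule B (SAP 5.3.1.5): the same difference, but missing if the start or the stop date is missing or partial.
- Inclusion in the 28-day table (SAP 4.4.1.2.3 and 4.4.1.3.2): onset from 0 to 28, or onset missing.
- SAE collection: from inclusion to 6 months after the last vaccination (Protocol 9.2.2.3.4), so onset after Day 28 is possible.

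**Result** (the event days are illustrative)

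| Event | Rule A: onset, 28-day table | Rule B: onset, 28-day table |
|---|---|---|
| Onset Day 10, stop known | 10, in | 10, in |
| Onset Day 10, stop missing | 10, in | missing, in |
| Onset Day 90, stop known | 90, out | 90, out |
| Onset Day 90, stop missing | 90, **out** | missing, **in** |
| Start missing | missing, in | missing, in |

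Among events that begin after vaccination, the rules differ on table membership only when onset is known to be after Day 28 and the stop date is missing or partial. Within Days 0 to 28, Rule B only loses the onset category. SAEs that began before vaccination are left out of this argument.

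**Does 5.3.1.5 cover SAEs?** It speaks of unsolicited AEs. Protocol 9.2.2.1 obtains the non-serious class by removing SAEs from unsolicited AEs, so the wider term includes them. The neighbouring SAP 5.3.1.4 says non-serious when it means the narrower class.

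**How much follow-up lies after Day 28?** Dose 2 was planned 6 months (±20 days) after dose 1 (Protocol 5.1.4, Visit 4). Assume 6 months = 183 days, with Days 0 to 28 counting as 29 days:

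- on schedule: 183 − 29 = 154; 154/183 = 84.2%
- dose 2 20 days early: 163 − 29 = 134; 134/163 = 82.2%
- dose 2 20 days late: 203 − 29 = 174; 174/203 = 85.7%

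Most of the time between the doses lies outside the 28-day window, so a late SAE onset is an ordinary case. These are shares of follow-up time. They are not event counts and say nothing about how often stop dates are missing.

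**The case against.** The strongest reply is that SAE onset has its own section. SAP 4.4.1.3.2 sends the reader to 4.4.1.2.3 and not to 5.3.1.5, and a programmer who stays with it gets the right answer. Section 5.3.1 also names SAEs where it deals with them, in 5.3.1.1 and 5.3.1.2, and 5.3.1.5 does not. So the SAE consequence depends on how the scope of 5.3.1.5 is read. That stands as a limit. It does not remove the conflict, because 5.3.1.5 is the SAP's dedicated section on missing dates and following it is just as reasonable.

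Second, three conditions must hold together: onset after Day 28, an incomplete stop date, and programming from 5.3.1.5. The protocol works against the second. SAE forms are updated with outcome (Protocol 10.2), and related SAEs that have not resolved are followed further (Protocol 5.1.4). A footnote in Protocol 9.2.2.3.3 treats AEs without a stop date as ongoing, but does not say how the date is coded. SAP 4.4.1.2.4 lists ongoing separately from blank and MD, so whether ongoing events are caught by 5.3.1.5 is unclear. Nothing in the documents shows that an affected SAE exists.

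Third, for non-serious AEs, which are collected over 28 days after each vaccination, membership of the table hardly changes; the effect is mainly on the display of onset. This is correct.

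Fourth, the error can only add a post-vaccination SAE to the 28-day table and never removes one from a table. The whole-study table and the separate listings allow recovery. This too is correct, and it is why the point is minor.

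**Conclusion.** The concern holds. The conflict in wording is certain: the stop date cannot bear on when an event began, and 5.3.1.5 says that it does. The misplacement of late SAEs is conditional. It needs 5.3.1.5 to be the section programmed, its term for unsolicited AEs to be read as including SAEs, and a stop date that is blank, coded MD or partial.

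The number of affected events cannot be estimated from the documents. The damage is limited to descriptive 28-day SAE counts, the matching seriousness and outcome summaries, and time-to-onset distributions. Whole-study SAE counts, the listings, the analysis sets and the non-inferiority tests do not change. Severity: minor.

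**What to change.** In SAP 5.3.1.5, delete the words *or stop*, so that time to onset is missing only when the start date or the vaccination date is missing or partial, as in 4.4.1.2.3. Add one sentence: a missing or partial stop date, or a ticked ongoing box, affects duration only, as in 4.4.1.2.4. This also settles how ongoing events are handled.

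With this change, the Day 90 SAE without a stop date has an onset of 90, stays out of the 28-day table and remains in the whole-study table. The cost is two words deleted and one sentence added; no new data, table or analysis is needed.

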5.3.1.6 Action Taken

Missing actions taken will remain missing and not be imputed.

5.3.2 Immunogenicity

No imputation of missing values and no statistical search for outliers will be performed (immunogenicity data will be considered as validated). LLOQ management will be performed as described in Section 4.3.2.1.

5.3.3 Efficacy

Not applicable.

5.4 Interim/Preliminary Analysis

The final analysis will be performed on data collected at the end of the study.

5.5 Determination of Sample Size and Power Calculation

Power calculation is based on initial sample size of the trial. 688 subjects were to be enrolled regardless of dengue baseline status: 344 subjects per treatment group (86 subjects per age group).

Considering a potential attrition rate of 10%, such sample size would provide 618 evaluable subjects in the PPAS of Tdap and CYD dengue vaccine (PPT and PPC). This will give, for the co-primary objectives, a global power over 90.0% for the testing of non-inferiority (based on SAS proc Power).

The following assumptions were considered for the non-inferiority on Tdap: an alpha level of 2.5% (one-sided hypotheses), a maximum acceptable difference of 0.176 for GMCs, and of 10% for seroprotection rates, and assuming the following rates and standard deviations (SDs):

- $T \geq 0.1$ IU/mL – 99% of subjects
- $D \geq 0.1$ IU/mL – 99% of subjects
- PT SD – 0.4
- FHA SD – 0.4
- PRN SD – 0.5
- FIM2+3 SD – 0.6

(based on TD519, TD506 and TD526 studies and on Keith S. Reisinger (4)).

The following assumptions were considered for the non-inferiority after the first dose of CYD dengue vaccine: an alpha level of 2.5% (one-sided hypotheses), a maximum acceptable difference of 0.301 for GMTs, and assuming a standard deviation of 1.0 for serotype 1, 0.8 for serotypes 2 and 3, 0.7 for serotype 4 (based on CYD22 and CYD47 studies conducted in Asia Pacific).

In addition, this sample size would have given for the non-inferiority after the third dose* of CYD dengue vaccine (on PPC3), considered as a secondary objective, a global power over 99.0% for the testing of non-inferiority (based on SAS proc Power).

The following assumptions were considered for the non-inferiority after the third dose* of CYD dengue vaccine: an alpha level of 2.5% (one-sided hypotheses), a maximum acceptable difference of 0.301 for GMTs, and assuming a standard deviation of 0.8 for serotypes 1 and 2, 0.7 for serotypes 3 and 4 (based on studies conducted in Asia Pacific).

* Analysis on the 3rd dose will not be done due to the early termination of study (cf. section 5.7)

Table 5.2: Powers for Non-inferiority between GMT/seroprotection for each antigen and serotype - Primary objective

Antigen/Serotype	Alpha	δ	Reference rate/SD	Power (%) for 309 evaluable subjects per group
D	0.025	10%	99%	> 99.9
T	0.025	10%	99%	> 99.9
PT	0.025	0.176	0.4	> 99.9
FHA	0.025	0.176	0.4	> 99.9
PRN	0.025	0.176	0.5	99.2
FIM2+3	0.025	0.176	0.6	95.4
Dengue serotype 1	0.025	0.301	1.0	96.2
Dengue serotype 2	0.025	0.301	0.8	99.7
Dengue serotype 3	0.025	0.301	0.8	99.7
Dengue serotype 4	0.025	0.301	0.7	> 99.9

Table 5.3: Powers for Non-inferiority between GMT for each serotype - Secondary objective

Serotype	Alpha	δ	Reference SD	Power (%) for 309 evaluable subjects per group
Dengue serotype 1	0.025	0.301	0.8	99.7
Dengue serotype 2	0.025	0.301	0.8	99.7
Dengue serotype 3	0.025	0.301	0.7	> 99.9
Dengue serotype 4	0.025	0.301	0.7	> 99.9

This sample size will also provide a 95% probability of observing an AE that has a true incidence > 0.87% in each group (N=344).

5.6 Data Review for Statistical Purposes

A review of the data is anticipated through the data review process led by Data Management before database lock.

5.7 Changes in the Conduct of the Trial or Planned Analyses

As protocol amendment 1 submitted following the IDMC recommendations to stop vaccinating seronegative individuals could not be implemented because of absence of response from the Philippines FDA, the Sponsor has decided to stop the trial following the study hold.

Therefore, the third dose of CYD dengue vaccine at V06 and the BS at V07 were not performed in any subject. The last phone call was replaced by a last safety follow-up visit before the end of the study (changes from study procedures table).

This early termination had an impact on the conduct of the trial and the planned analyses, as summarized below:

- 2.2 Secondary objectives: As no subjects received the third injection of the CYD Dengue vaccine, objectives associated to the third injection will not be assessed
- 4.2.1 Immunogenicity: As no subjects received the third injection of the CYD Dengue vaccine, endpoints and immunogenicity assessment methods associated to the third CYD vaccination are not applicable
- 4.2.2.2 CYD Dengue vaccine Seropositivity and other threshold: Seropositivity and threshold for the third CYD vaccination are not applicable
- 5.1.2 Hypotheses and Statistical Methods for secondary objectives:
 - Hypotheses and statistical methods on the Non-inferiority on CYD dengue vaccine after three doses are not applicable.
 - Descriptive analysis on CYD dengue vaccine will not be assessed after the third dose of CYD dengue vaccine
- 5.2.2 Per-protocol Analysis Set: As no subjects received the third injection of the CYD Dengue vaccination the Per-Protocol population on the 3rd CYD vaccination (PPC3) defined in protocol V1.0 will be removed and the Per-Protocol population on the 1st CYD vaccination (PPC1) will be renamed by PPC
- 5.2.2: Definition of the PPT and PPC were revised in order to integrate an additional deviation after IDMC recommendation and based on new label indication. Subjects seronegative at baseline will be excluded from the 2 populations.
- 5.2.5 Population Used in Analysis:
 - According to the new definition of the Per-Protocol Analysis Set, the main immunogenicity analyses (non-inferiority tests) will be reduced to the dengue immune subjects (seropositive) and analyzed by the group which they were randomized.
 - All the other immunogenicity and safety analysis will be performed according to the baseline dengue status
- 5.4 Interim /Preliminary Analysis:

- The first interim analysis scheduled on results obtained after a partial database lock of data collected up to the 28 days post first dose of CYD dengue vaccine at V03, M2) was not done due to the hold of the study.
 - The potentially second interim analyses scheduled on results collected up to the 28 days after the third dose CYD dengue vaccine at V06, M13 was not performed because no subjects received the third CYD dose.
 - Only one final statistical analysis will be performed.
- 5.5 Determination of the sample size and power calculation:

Considering a potential attrition rate of 10%, it was initially planned that such sample size would provide 618 evaluable subjects in the PPAS of Tdap and CYD dengue vaccine (PPT and PPC). This sample size (based on SAS proc Power) targeted a global power over 90.0% for the non-inferiority testing corresponding to the co-primary objectives (i.e., after the booster dose of Tdap and after the first dose of CYD), and over 99.0% for the non-inferiority corresponding to the secondary objective (ie, testing after the third dose of CYD dengue vaccine).

However, with early termination of the study, since the number of evaluable subjects will be reduced (ie, number of dengue seropositive subjects in PPT and PPC), reducing global power to 80% may be considered. Thus, the non-inferiority testing will be carried out only if a global power of at least 80% for the co-primary objectives can be attained (i.e., if the number of evaluable subjects is at least 510 for the co-primary objectives and 324 for the secondary objective). (table 5.4 and 5.5)

Table 5.4: Powers for Non-inferiority between GMT/seroprotection for each antigen and serotype - Primary objective

Antigen/Serotype	Alpha	δ	Reference rate/SD	Power (%) for 309 evaluable subjects per group	Power (%) for 255 evaluable subjects per group
D	0.025	10%	99%	> 99.9	> 99.9
T	0.025	10%	99%	> 99.9	> 99.9
PT	0.025	0.176	0.4	> 99.9	> 99.9
FHA	0.025	0.176	0.4	> 99.9	> 99.9
PRN	0.025	0.176	0.5	99.2	97.8
FIM2+3	0.025	0.176	0.6	95.4	91.1
Dengue serotype 1	0.025	0.301	1.0	96.2	92.4
Dengue serotype 2	0.025	0.301	0.8	99.7	98.9
Dengue serotype 3	0.025	0.301	0.8	99.7	98.9
Dengue serotype 4	0.025	0.301	0.7	> 99.9	99.8
Global power				90%	80%

Table 5.5: Powers for Non-inferiority between GMT for each serotype - Secondary objective

Serotype	Alpha	δ	Reference SD	Power (%) for 309 evaluable subjects per group	Power (%) for 162 evaluable subjects per group
Dengue serotype 1	0.025	0.301	0.8	99.7	96.4
Dengue serotype 2	0.025	0.301	0.8	99.7	96.4
Dengue serotype 3	0.025	0.301	0.7	> 99.9	99.0
Dengue serotype 4	0.025	0.301	0.7	> 99.9	99.0
Global power				99%	80%

This sample size will also provide a 95% probability of observing an AE that has a true incidence > 0.87% in each group (N=344).

TLFs document will be done on collected data.

6 References List

- 2 Newcombe RG. Two-sided confidence intervals for the single proportion: comparison of seven methods. *Statistics in Medicine*. 1998; 17:857-72
- 3 Newcombe R. G. Interval estimation for the difference between independent proportions: comparison of eleven methods. *Statistics in Medicine* 17: 873-890, 1998.
- 4 Reisinger KD. Safety, Tolerability, and Immunogenicity of Gardasil Given Concomitantly with Menactra and Adacel. *Pediatrics* 2010;125;1142
